3.9.2 Off-Study Criteria

- Completion of post-treatment week 16 off-study visit
- Participant requests to be withdrawn from study
- Death

3.9.3 Off Protocol Therapy and Off Study Procedure

3.9.3.1 Clinical Center Off Protocol Therapy and Off-Study Procedure

Authorized staff must notify Central Registration Office (CRO) when a subject is taken off protocol therapy and when a subject is taken off-study. A Participant Status Update Form from the web site (<http://home.ccr.cancer.gov/intra/eligibility/welcome.htm>) main page must be completed and sent via encrypted email to: NCI Central Registration Office [contact].

3.9.3.2 Participating Site Off Protocol Therapy and Off-Study Procedure

The Participant Status Update Form will be supplied by the NIAMS study coordinator. Send the completed form to the NIAMS study coordinator.

3.10 BASIC AND CLINICAL SCIENCE RESEARCH PLAN

3.10.1 Characterize and dissect inflammatory pathways in participant lesional skin and peripheral blood mononuclear cells

3.10.1.1 Immunohistochemical studies

Immunohistochemistry studies will be utilized to characterize the hematopoietic inflammatory infiltrate in lesional skin, including neutrophils (neutrophil elastase and CD15), myeloid dendritic cells (blood dendritic cell antigen [BDCA]-1, CD11c, BDCA-3), macrophages (CD163) and T lymphocytes (CD3).

Two-color immunofluorescence will be performed to determine CARD14⁺ cells (e.g., CARD14 versus CD11c, CARD14 versus CD163)⁵⁵⁻⁵⁷.

Abbreviated Title: Anakinra in pustular dermatoses

Version Date: December 12, 2018

3.10.1.2 Global gene expression studies

Lesional and nonlesional skin biopsies obtained before and after treatment with anakinra will be assayed for gene expression profiles with microarray assays. Genes associated with immune dysregulation and cell differentiation will be assessed and compared between patients. Gene expression will be confirmed by reverse transcriptase polymerase chain reaction (RT-PCR) and quantitative RT-PCR for low-expressing cytokines.

For patients with systemic inflammation characterized by fever, marked leukocytosis and/or elevated acute phase reactants, we will perform gene expression studies on peripheral blood mononuclear cells (PBMCs) before and after treatment with anakinra.

These profiles will be compared with gene expression profiles from lesional skin in patients with known DIRA (n=2), CARD14 mutations (n=3), and familial psoriasis (n=5). Additional analytic approaches will include Ingenuity Pathways Analysis (IPA), and Gene Set Enrichment Analysis (GSEA)^{55, 58, 59}.

Genomics studies will not be performed on this protocol. Genomics studies for pustular dermatoses will be performed on protocol 17-I-0016. At the time of enrollment, patients will be offered simultaneous enrollment in protocol 17-I-0016. (Section 5.2)

3.10.1.3 Cytokine studies

We will perform skin and serum studies before and after anakinra therapy to assess levels of inflammatory cytokines including IL-1b, IL-6, IL-8, IL-17, IL-21, IL-22, IL-23, G-CSF and TNF using RT-PCR Luminex assay.

3.10.2 Evaluate systemic inflammation in participants with pustular dermatoses using imaging modalities and biomarkers of cardiometabolic disease

3.10.2.1 Fluoro-Deoxy-Glucose PET CT Imaging for Body Metabolism

We will utilize a technique for quantifying the extent of atherosclerosis in the aorta by combining standard uptake values (SUVs) in the aortic wall obtained using FDG-PET with volumetric data provided by CT^{60,61}. FDG uptake will be measured in all six segments of the aorta by calculating the mean combining SUVs for each segment. On each axial CT image, region-of-interest tracings along the inner and outer wall contours of the aorta are created. The average SUVs are then multiplied by the wall volume to calculate the total amount of vascular inflammation for each segment of the aorta. This total amount of vascular inflammation of each aortic segment can be used as an indicator of the extent of the atherosclerotic process by combining the functional and structural data provided by FDG-PET and CT.

Subjects will fast for six hours prior to imaging. Blood glucose will be checked and should be in the 100-160 mg/dL range to ensure an optimum study. The patient is injected with 10 mCi of 18-Fluoro-Deoxy glucose (FDG) and then rests for 60 minutes. The effective radiation dose of two 10 mCi injections of FDG is 2.6 rem. The subject will be positioned in a 16-slice PET CT scanner (GE, Discovery ST). The CT images acquired as part of the PET CT examination will be acquired using a low dose technique during quiet breathing. The CT images will allow for attenuation correction of the PET emission data, and will aid in the accurate anatomical

Abbreviated Title: Anakinra in pustular dermatoses

Version Date: December 12, 2018

localization of sites of radiotracer uptake seen on PET images. The scanning time is typically 45 minutes. The CT and PET images are co-registered and can be viewed and interpreted.

The presence of brown fat is inferred from the following:

- FDG uptake in known usually symmetric distribution in the body
- Corresponding CT appearances consistent with fat at a site of FDG uptake

Whole body metabolism can be assessed by visual inspection of scout images and then quantified using standardized uptake volumes (SUV).

3.10.2.2 Evaluating biomarkers of cardiometabolic disease

We will evaluate biomarkers of cardiovascular disease by assaying pro-atherogenic lipoproteins via nuclear magnetic resonance spectroscopy (NMR), and high density lipoprotein (HDL) function via HDL cholesterol efflux capacity.

3.10.3 Evaluate keratinocyte responses to targeted inflammatory stimuli including infectious agents and danger molecules.

3.10.3.1 Characterize response to Toll-like receptor (TLR) stimulation

Our preliminary data shows that keratinocytes from patients with monogenic forms of pustular diseases not only produce higher levels of proinflammatory cytokines and chemokines in response to stimulation, but also demonstrate hyper- and parakeratosis histologically, thus indicating abnormal differentiation and abnormal apoptosis. We will create keratinocyte cell lines to assess whether keratinocytes from patients with pustular lesions have abnormal responses to TLR stimulation. We have made keratinocyte cell lines from skin biopsies from both healthy individuals and patients with monogenic pustular skin diseases (healthy controls, n=6; DIRA, n=2; CARD14, n=1). We will create keratinocyte cell lines from study participants with genetically-undefined pustular diseases. The keratinocyte cell lines will be immortalized as recently described in the presence of feeder cells and a ROCK-inhibitor.⁶²

Keratinocytes from healthy controls, patients with monogenic forms of pustular disease, and patients with genetically-undefined pustular diseases will be exposed to a panel of TLR stimulants. We will use gene expression profiling to assess the impact of TLR stimulation on cell differentiation.

3.10.3.2 Compare affected and unaffected keratinocytes and fibroblasts with those of patients with monogenic pustular diseases and genetically-undefined pustular diseases in an organotypic raft culture system

We will study signaling pathway effects on keratinocyte proliferation and differentiation in an environment that closely mimics human epidermis. The organotypic raft culture system has been shown to mimic the functional alterations observed in inflammatory disease⁶³. Immortalized keratinocytes (as described above) will be used to generate rafts to examine the response of these cells to stimuli from cytokines and TLR agonists.

Abbreviated Title: Anakinra in pustular dermatoses

Version Date: December 12, 2018

We will evaluate inflammatory and differentiation properties in keratinocytes from study participants. Immunohistochemical techniques will be applied to raft cultures to evaluate alterations in markers of proliferation (PCNA, Ki67) and differentiation (epidermal differentiation markers including loricrin, filaggrin, involucrin, keratin 1, keratin 10) between unaffected controls and patient samples. Preliminary characterization by western blot analysis of immortalized keratinocytes from unaffected controls differentiated in culture with calcium⁶⁴ indicate that this methodology is also applicable for these samples.

4 CONCOMITANT MEDICATIONS/MEASURES

No drug-drug interaction studies with anakinra in human subjects have been conducted. Toxicological and toxicokinetic studies in rats did not demonstrate alterations in the clearance or toxicological profile of either methotrexate or anakinra when the two agents were administered together. In two studies of concurrent etanercept and anakinra therapy, patients were treated for up to 24 weeks and a 7% rate of serious infections was observed, which was higher than when either agent was used alone. Two percent of patients (3/139) treated concurrently with anakinra and etanercept developed neutropenia ($ANC < 1 \times 10^9/L$). Patients enrolled into this study will be required to discontinue etanercept (Enbrel[®]), or other TNF-inhibitor therapy, including infliximab (Remicade[®]), golimumab (Simponi[®]) and adalimumab (Humira[®]), certolizumab (Cimzia[®]), and other TNF-inhibiting agents such as thalidomide at least three half lives prior to initiation of anakinra therapy because of a potential increased risk of infection (**APPENDIX A: FORBIDDEN DRUGS**). All medication changes will be recorded in the patient daily diary.

4.1 SUPPORTIVE CARE

Patients will be screened thoroughly and will be instructed by medical providers to detect and report early signs of side effects related to anakinra. Patients will receive instructions on monitoring, recording, and reporting side effects or adverse events. Should subjects experience an adverse event, they will be instructed to contact the study team immediately and to anticipate a clinic visit for evaluation and possible treatment.

4.1.1 NIH Patients

Communication and consultation with physicians and nurses is available 24 hours a day, 7 days a week through the nursing unit of the NIAMS Dermatology Clinic or the NIH page operator at [contact]. When possible, subjects requiring supportive care will be evaluated at the NIH. If a subject is unable to be seen at the NIH, telephone consultation will be available, as described above, to assist other practitioners involved in the patient's care.

4.1.2 UCSF Patients

Communication and consultation with physician and study coordinator is available 24 hours a day, 7 days a week through the UCSF Dermatology Clinic, the UCSF page operator or the confidential patient portal service, MyChart. When possible, subjects requiring supportive care will be evaluated at UCSF. If a subject is unable to be seen at UCSF, telephone consultation will be available, as described above, to assist other practitioners involved in the patient's care.

Abbreviated Title: Anakinra in pustular dermatoses

Version Date: December 12, 2018

5 BIOSPECIMEN COLLECTION

5.1 CORRELATIVE STUDIES FOR RESEARCH

The research nurse will be responsible for coordinating transport of biospecimen samples collected throughout the study.

5.1.1 Blood (Clinical and Research Samples)

Blood will be obtained from each patient during the initial and subsequent visits. All blood volumes to be drawn will remain within the NIH Clinical Center guidelines for adult patients. Only clinical laboratory and/or microbiology results will be returned to the patient or their designated primary care provider (PCP). In rare instances, blood drawing limit may exceed the expected volume as a result of loss or damage of blood samples, repeating the tests in order to validate unusual or erroneous results, will not exceed the limits set forth by the NIH CC MEC policy. The amount of blood drawn from adults for research purposes shall not exceed 10.5 mL/kg or 550 mL, whichever is smaller, over any eight week period. Additionally, aliquots of blood may be coded and shared with other collaborating researchers/investigators, under the auspices of appropriate material transfer agreements.

5.1.1.1 Clinical bloods

Blood samples will be analyzed for standard medical evaluations as outlined in Section 2.

5.1.1.2 Research bloods

Research blood will be drawn to examine serologic and immunological markers, including but not limited to cytokines, cardiometabolic markers including fasting insulin and glucose and gene expression studies (see section 3.10.1.2).

5.1.1.3 Research biopsies

At the investigator's discretion, research skin punch biopsies will be collected from lesional and nonlesional skin at baseline and week 12 to perform immunohistochemistry studies, cytokine studies and gene expression studies. Keratinocyte responses to infectious and inflammatory stimuli will be assessed. Keratinocytes will also be used to make cell lines which will then be used to study keratinocytes inflammatory and differentiation properties in vitro.

5.2 SAMPLE STORAGE, TRACKING AND DISPOSITION

Please refer to protocol 17-I-0016 for details.

Abbreviated Title: Anakinra in pustular dermatoses

Version Date: December 12, 2018

Whole blood, blood products, tissue, and RNA from all subjects will be stored indefinitely in the laboratories of [name] and [name], and coded by study date and number. Patient samples will be identifiable using a database that is only accessible to the researchers intimately involved with the protocol. The samples themselves will not have direct patient identifiers.

Effective with amendment J, all patients will be offered simultaneous enrollment in protocol 17-I-0016, which aims to comprehensively evaluate patients with inflammatory multi-system diseases clinically, genetically, immunologically, and endocrinologically, and evaluate long term outcomes and biomarkers. If the patient consents to both studies, data collected on protocol 17-I-0016 will be correlated with data collected on our protocol.

NOTE: Prior to amendment J, subjects were offered simultaneous enrollment onto protocol 03-AR-0173, for the purposes described above. However, data from protocol 03-AR-0173 has been transferred to protocol 17-I-0016.

If the patient withdraws consent, the participant's data will be excluded from future distributions, but data that have already been distributed for approved research use will not be able to be retrieved.

All specimens obtained in the protocol are used as defined in the protocol. Any specimens that are remaining at the completion of the protocol will be stored in the conditions described below. The study will remain open so long as sample or data analysis continues. Samples from consenting subjects will be stored until they are no longer of scientific value or if a subject withdraws consent for their continued use, at which time they will be destroyed. The PI will report any loss or destruction of samples to the NIH Intramural IRB as soon as he is made aware of such loss.

The PI will report destroyed samples to the IRB if samples become unsalvageable because of environmental factors (ex. broken freezer or lack of dry ice in a shipping container) or if a patient withdraws consent. Samples will also be reported as lost if they are lost in transit between facilities or misplaced by a researcher. Freezer problems, lost samples or other problems associated with samples will also be reported to the IRB, the NCI Clinical Director, and the office of the CCR, NCI.

Samples at NIH will be ordered in CRIS and tracked through a Clinical Trial Data Management system. Should a CRIS screen not be available, the CRIS downtime procedures will be followed. Samples will not be sent outside NIH without IRB notification and an executed MTA.

6 DATA COLLECTION AND EVALUATION

6.1 DATA COLLECTION

Data will be collected by investigators during visits and recorded in the patient's permanent medical record. Data will be entered into the C3D database. Protocol-specific case report forms will be developed and completed by the clinical teams. Data collection forms may include the clinical and laboratory information obtained from standard clinical evaluations at study entry,

Abbreviated Title: Anakinra in pustular dermatoses

Version Date: December 12, 2018

organ-specific scales, selected research laboratory data and the follow-up outcomes that are necessary for determination of primary and secondary endpoints.

Personal identifiers will not be used when collecting and storing data. An enrollment log will be maintained in the regulatory binder/file which is the only location of personal identifiers with unique subject identification number.

The PI will be responsible for overseeing entry of data into an in-house password protected electronic system and ensuring data accuracy, consistency and timeliness. The principal investigator, associate investigators/research nurses and/or a contracted data manager will assist with the data management efforts. All data obtained during the conduct of the protocol will be kept in secure network drives or in approved alternative sites that comply with NIH security standards. Primary and final analyzed data will have identifiers so that research data can be attributed to an individual human subject participant.

All adverse events, including clinically significant abnormal findings on laboratory evaluations, regardless of severity, will be followed until return to baseline or stabilization of event. Patients will be followed for adverse events for 28 days after removal from study treatment or until off-study, whichever comes first.

An abnormal laboratory value will be recorded in the database as an AE **only** if the laboratory abnormality is characterized by any of the following:

- Results in discontinuation from the study
- Is associated with clinical signs or symptoms
- Requires treatment or any other therapeutic intervention
- Is associated with death or another serious adverse event, including hospitalization.
- Is judged by the Investigator to be of significant clinical impact
- If any abnormal laboratory result is considered clinically significant, the investigator will provide details about the action taken with respect to the test drug and about the patient's outcome.

End of study procedures: Data will be stored according to HHS, FDA regulations and NIH Intramural Records Retention Schedule as applicable.

Loss or destruction of data: Should we become aware that a major breach in our plan to protect subject confidentiality and trial data has occurred, the IRB will be notified.

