3 STUDY IMPLEMENTATION

3.1 STUDY DESIGN

This will be a phase 2, open label, prospective interventional 16-week dose titration study. Patients will complete a daily diary during the entire 16-week study course. Patients will be instructed to score the severity of rash, pustules, itch, skin pain, joint pain and overall well-being into their daily diaries. They will also document fever and doses of medications in their diaries.

(APPENDIX B: PATIENT)

At the baseline visit, clinical assessments, and laboratory, histopathologic and subjective data will be collected. All enrolled patients will initially receive treatment with anakinra 100 mg/day via self-administered subcutaneous injection. The first dose of anakinra will be administered under supervision in the clinic.

At week 4, disease response will be assessed by clinical exam, laboratory markers and evaluation of patient diaries that are returned to clinic. Determination for dose escalation will be made based on week 4 assessments. Those patients who do not achieve complete disease clearance with initial anakinra dosing will be increased to the next incremental dose level (see Section 3.1.2).

At week 8, patients will return for clinical evaluation and patients who do not achieve complete disease clearance on anakinra have the option of dose escalation up to the next incremental dose level. All patients will stop anakinra at week 12.

Patients will return for an Off Study visit at week 16, approximately 28 days after their final dose is administered. Considering personal/work/travel/other obligations, a period of no more than 1 week before or after the Week 4, 8, or 12 visits, and 2 weeks before or after the Week 16 visit may be permitted.

Total body photographs will be taken at baseline, week 4, week 8, week 12 and week 16 (at the investigator's discretion).

With the patient's consent, and at the discretion of the investigator, a skin biopsy for research will be taken at baseline and week 12. Skin biopsies will be taken from lesional and non-lesional skin. Non-lesional skin will be obtained for the purpose of comparison with lesional skin in immunohistochemistry, cytokine and gene expression studies, as well as in vitro keratinocytes studies.

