Research blood sampling		X						X		
Rheumatology Consultation including ACR assessment ^e		X		X		X		X		X
Cardiometabolic evaluation including electrocardiogram		X						X		
Ophthalmologic examination		X						X		
Gastrointestinal consultation		X						X		

Abbreviated Title: Anakinra in pustular dermatoses

Version Date: December 12, 2018

	Screening ≤8 weeks prior to enrollment	Baseline- up to drug initiation ^a	Weeks 1, 2, 3 (+/- 3 days)	Week 4 (+/- 1 week)	Weeks 5, 6, 7 (+/- 3 days)	Week 8 (+/- 1 week)	Weeks 9, 10, 11 (+/- 3 days)	Week 12 (+/- 1 week): End of Treatment	Weeks 13, 14, 15 (+/- 3 days)	Week 16 (+/- 2 weeks): Post Therapy Follow- up ^a
QOL/questionnaires ^f		X		X		X		X		X
Daily scoring diary		Start Day 0		X-----X						
AE Monitoring		START	X	X	X	X	X	X	X	X

^a Additional clinical labs may be obtained as indicated at baseline and follow up visits

^b As indicated in section 10.3, all subjects at NIH will be offered the opportunity to complete an NIH advanced directives form. This should be done preferably at baseline but can be done at any time during the study as long as the capacity to do so is retained. The completion of the form is strongly recommended, but is not required.

^c If escalation criteria are met (see Section 3.2)

^d Within 8 weeks of enrollment

^e If the rheumatology consult is done at Week 0, the patient will be seen again at Week 12. If there is evidence of joint disease, patients will be strongly encouraged to have rheumatology consult during all clinic visits (Weeks 0, 4, 8, 12 and 16)

^f QOL/questionnaires (see Section 3.4)

^g Skin biopsy for hematoxylin and eosin staining to confirm diagnosis if prior confirmational biopsy has not been performed

^h Performed at the investigator's discretion for research purposes

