3.9 CRITERIA FOR REMOVAL FROM PROTOCOL THERAPY AND OFF STUDY CRITERIA

Prior to documenting removal from study, effort must be made to have all subjects complete a safety visit approximately 28 days following the last dose of study therapy.

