3.9.1 Criteria for removal from protocol therapy

- Completion of 12-week anakinra therapy
- Noncompliance with protocol procedures
- Pregnancy
- Participant requests to be withdrawn from active therapy
- Non-allergic toxicity or observed allergic reaction to anakinra
- Investigator discretion
- Positive pregnancy test
- Death

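### A week-16 visit held early, as the protocol allows, can end collection of new adverse events 14 days after the last dose, half the roughly 28 days intended

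*Combined protocol and SAP*

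**What the plan says.** Five provisions of the combined protocol and SAP bear on this point.

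- **End of treatment.** Section 3.1: "All patients will stop anakinra at week 12". Section 3.9.1 lists "Completion of 12-week anakinra therapy" as a reason for leaving protocol therapy.
- **Off-study visit.** Section 3.1 places it at week 16, "approximately 28 days after their final dose is administered", and then adds that "2 weeks before or after the Week 16 visit may be permitted". The calendar in section 3.6 carries the same window: "Week 16 (+/- 2 weeks): Post Therapy Follow- up".
- **Going off study.** Section 3.9.2 lists "Completion of post-treatment week 16 off-study visit" as a criterion.
- **Adverse-event follow-up.** Section 6.1: "Patients will be followed for adverse events for 28 days after removal from study treatment or until off-study, whichever comes first".
- **Safety visit.** Before removal from study is documented, section 3.9 calls for effort to have each patient complete a "safety visit approximately 28 days following the last dose of study therapy".

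Section 3.1 also schedules adverse-event calls at weeks 13, 14 and 15, each with a 3-day margin. Section 6.1 follows events already identified until they return to baseline or stabilize.

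**The concern.** The protocol aims for about 28 days of safety follow-up after the last dose and says so in sections 3.1, 3.9 and 6.1. But section 6.1 takes the earlier of 28 days and off-study, and the visit that triggers off-study can itself be moved 2 weeks earlier. A scheduling convenience can therefore halve the period in which new events are collected, even for a patient who completes the study.

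Safety and toxicity are a secondary objective (section 1.1.2), and section 1.2 names infection among the most serious risks of anakinra. A new infection or other event that begins after an early off-study visit but within 28 days of the last dose need not be collected. Section 3.1.1 does not help, because it makes patients evaluable for toxicity only until study participation ends, which is the same early point.

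**Working it through.** **Inputs**

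- Last dose: week 12 = 12 × 7 = day 84 (sections 3.1 and 3.9.1).
- Off-study visit: week 16 = 16 × 7 = day 112, allowed 14 days early or late (sections 3.1 and 3.6).
- Follow-up rule: the smaller of 28 days and the time to off-study (section 6.1), with off-study reached on completing the week-16 visit (section 3.9.2).
- Infection over 6 months on anakinra: 39% any, 2% serious (section 11.1.2).
- Accrual ceiling: 30 patients (section 8).

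**The plan's own figure.** At the nominal visit, 112 - 84 = 28 days, which agrees with the protocol.

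**Length of new-event collection by visit date**, for a week-12 last dose:

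- Visit at week 14: day 98 - day 84 = 14 days, so 28 - 14 = 14 days are lost.
- Visit at week 15: day 105 - day 84 = 21 days, so 7 days are lost.
- Visit at weeks 16 to 18: 28 days, nothing lost.

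**Do the telephone calls cover the gap?**

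- Week 13: 91 ± 3 = days 88 to 94, before a day-98 visit.
- Week 14: 98 ± 3 = days 95 to 101, around it.
- Week 15: 105 ± 3 = days 102 to 108, wholly after it. Even at its latest it reaches only 108 - 84 = day 24 after the last dose.

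No call is scheduled at day 28.

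**Events at stake.** As an upper bound, assume that all 30 patients are seen on day 98 and that the on-drug rates continue unchanged after stopping. Take 6 months as 182 days.

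- Proportional, 30 × rate × 14/182: serious 30 × 0.02 × 14/182 = 0.046; any 30 × 0.39 × 14/182 = 0.90.
- Constant hazard, 30 × [1 - (1 - rate)^(14/182)]: serious 30 × (1 - 0.98^(14/182)) = 0.047; any 30 × (1 - 0.61^(14/182)) = 1.12.

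The documents do not say how often the visit will be held early. Over an assumed range:

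- 10% seen on day 98 (3 of 30): 0.005 serious; 0.09 to 0.11 any.
- 50% seen on day 98 (15 of 30): 0.023 serious; 0.45 to 0.56 any.

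**The case against.** The case for leaving the text alone has five parts.

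- **Most of these infections are background.** Section 11.1.2 gives 37% any infection and 1% serious infection on placebo. Using only the excess over placebo, the upper bound falls to 30 × 0.02 × 14/182 = 0.046 infections of any kind and 30 × 0.01 × 14/182 = 0.023 serious ones. This is right about drug-attributable harm. It is not the number of events missed, because section 7.1.1 defines adverse events regardless of cause.
- **Serious events have another route.** Sections 7.2.1 and 7.3 require reporting of serious adverse events, most deaths and unanticipated problems, with no end date tied to off-study, and section 4.1 tells patients to contact the team at once. This narrows the gap, mainly to non-serious events. But it depends on the team learning of the event, and no scheduled contact provides for that after an early off-study visit.
- **Section 3.9 and the week-15 call may delay off-study in practice.** Section 3.9 does point to day 28 before removal is documented, and nothing expressly cancels the week-15 call. If that call is made, 4 to 10 of the 28 days remain uncovered instead of 14. But section 3.9 asks only for effort, and under section 6.1 a call after off-study falls outside the collection period.
- **The early visit is optional and the rule is deliberate.** Both are true, and 14 days is the worst case.
- **A telephone call cannot replace laboratory tests.** This stands: a call will not find silent neutropenia. The blood tests would still be done at the early visit, as they are now.

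**Conclusion.** The concern holds. The protocol's own windows, off-study criterion and follow-up rule permit 14 days of new-event collection where about 28 are intended, and no other provision sets a floor. The 14-day figure assumes a last dose on day 84, a visit on the earliest permitted day, and off-study status on completion of that visit.

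The consequence is small. At most about 0.05 serious infections and 0.9 to 1.1 infections of any kind would be missed, if all 30 patients are seen on day 98 and on-drug rates persist. With 10% to 50% seen then, the figures are 0.005 to 0.02 serious and 0.09 to 0.6 of any kind. Events already open at the visit are still followed. The study has a single arm, so no between-group comparison is affected, and the primary endpoint is assessed at week 12, before the gap begins. This is an inexpensive improvement in safety capture and does not threaten the trial's conclusions.

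**What to change.** Amend section 6.1 so that, unless the patient withdraws from the study or dies, new adverse events are collected through at least day 28 after the actual last dose, dropping the cut-off at an earlier off-study date for everyone else. Amend section 3.9.2 to match: when the week-16 visit is held before day 28, the patient goes off study only after a closing telephone contact on or after day 28. Deferring off-study status is essential; otherwise the call would come after collection had formally ended.

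The cost is at most one extra call per patient seen early, and an off-study date up to about 14 days later for those patients. Dosing, visit windows and the primary endpoint do not change.
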